#### 2.2 Outcome Measures

### 2.2.1 Phase I

- Selumetinib and metabolite serum levels pre-dose and at 2 and 6 hours on day 1 and pre-dose on day 15.
- HAART drug levels pre-dose on days 1, 15 and at 12 weeks.

#### 2.2.2 Phase I & II

- Toxicity assessed by CTCAE v 4.0 criteria (see Appendix 4).
- Number of selumetinib cycles completed and PFS data will be collected as supportive data out to
   12 months from the last patient completing study treatment.
- Objective response rates assessed using ACTG criteria (see Appendix 1).
- Progression free survival rate 6 months from the start of study treatment assessed using ACTG criteria.
- Human immunodeficiency virus (HIV) control by HIV-1 viral load pre-treatment and weeks 3, 6, 12 and 18, and CD4 counts pre-treatment and at weeks 9 and 18.
- Pharmacodynamic measures of selumetinib in combination with HAART assessed by:
  - Serum concentrations of angiogenesis markers including serum Ang-2, IL-6 and VEGF assessed by ELISA pre-study and on weeks 3, 6, 12 and 18.
  - Biopsies pre-study and at week 6 to assess pERK levels in tumour tissue and other downstream markers including c-myc, c-fos, changes in apoptosis markers such as Bad and Bcl-2, and adaptive changes in PI3K/Akt and other MAPK pathways such as JNK and p38.
- Analysis of peripheral blood mononuclear cells (PBMCs) collected in a sub-study at selected centres pre-treatment and at weeks 9 and 18.
  - Levels of pERK, down-stream targets c-fos and c-myc, and key apoptotic proteins Bad and Bcl-2 will be assessed by Western blotting of lysed viable PBMCs.
  - PBMCs will be challenged with TLR4 and 9 agonists and production of IL-1 $\beta$ , TNF- $\alpha$ , IL-6, IL-10, IL-12 and type 1 interferon will be measured by cytometric bead array of culture supernatants.
  - o ROS production by PBMCs will be measured by flow cytometry using dichlorofluorescein (DCF) and cell survival assessed by Annexin V-PE/TO-PRO3 staining and flow cytometry.

Page 18 of 61

# 3 TRIAL DESIGN

This is an open-label multi-centre phase I/II study. In phase I, patients will be recruited to establish the dosage, safety, pharmacokinetics and pharmacodynamics of selumetinib in combination with HAART in KS using a 3 + 3 dose escalation algorithm. In phase II, efficacy will be assessed by best objective tumour response in a single patient cohort according to a two stage Simon design. Potential patients will be identified by the treating oncologist or referring communicable disease team (i.e. Infectious Disease or Genito-Urinary Medicine).

### 3.1 Phase I

75 mg bd is the recommended dose for phase II monotherapy studies. Interactions between selumetinib and HAART are not anticipated. Therefore for this study the starting dose of selumetinib is 50 mg PO bd in combination with HAART. The dose of selumetinib will be escalated in fixed increments thus:

Dose level	Dose of Selumetinib PO, (total daily dose)	Minimum number of patients
-1	75 mg od (75 total)	
1 (starting)	50 mg bd (100 total)	3
2	75 mg bd (150 total)	3
3	100 mg bd (200 total)	3

Three patients will be enrolled at the starting dose of 50mg bd. All three will be followed for at least one completed cycle (21 days) and a Safety Review Committee teleconference to discuss the dose escalation will occur before opening new cohorts. Subsequent enrolment will be based on observed Dose Limiting Toxicities (DLT):

- If 0/3 patients exhibit DLT, dose escalate to level 2 in a new cohort of patients
- If 1/3 patients exhibit DLT at the starting dose, expand the cohort to a total of 6 patients
  - o If no further DLT events are seen, dose escalates to level 2 in a new cohort of patients.
  - o If 1 or more further DLT events are seen (i.e. 2 or more from 6 patients) the dose of selumetinib will be de-escalated and 3 patients recruited to a new cohort at the -1 dose
- If 2/3 patients exhibit dose limiting toxicity at the starting dose level
  - o The dose will be de-escalated to dose level -1, and 3 patients recruited to the lower dose.
  - If 1/3 patients exhibit DLT at the new lower dose level this cohort will expand to a total of 6 patients.
- The dose will be escalated to dose level 3 only if no patient exhibits a DLT at dose level 1 or 2 and pharmacokinetic data show inadequate selumetinib serum levels at lower dose levels.

Patients recruited to 50mg bd who experience no toxicity in cycle 1 can be dose escalated to 75mg bd selumetinib in subsequent cycles.

Patients who continue to respond to selumetinib following completion of 6 cycles of therapy will be offered the option of continuing selumetinib. In this instance a clinical investigator at sites should email the SCART Trial Office, outlining the clinical benefit experienced by the patient when the patient has reached the C5D22/C6D1 visit. This will be forwarded to AstraZeneca for approval. The approval will then be communicated to sites. Patients who have been shown to derive benefit from the selumetinib and HAART combined therapy at one year should be continued on this regimen as long as their risk: benefit analysis, in the opinion of the treating physician, favours the continuation of treatment and with approval from AstraZeneca. In this instance sites should contact the SCART Trial Office.

# 3.1.1 Dose Limiting Toxicity (DLT)

For determination of the Maximum Tolerated Dose (MTD), DLTs will be assessed during Cycle 1 in Phase I only, (i.e. up to the time of Cycle 2 day 1 assessment). Toxicity will be graded using CTCAE version 4.0 (Appendix 4). Any DLT must be considered at least possibly related to selumetinib. DLT is defined as follows:

# 3.1.1.1 Haematologic

- Absolute neutrophil count (ANC) < 1.0 x 10^9/L
- Febrile neutropenia (ANC < 1.0 x 10^9/L, fever ≥ 38°C)
- Platelets < 50 x 10^9/L
- Bleeding thought to be due to thrombocytopenia

# 3.1.1.2 Non-Haematologic

- Diarrhoea > Grade 3 despite optimal loperamide use
- Rash ≥ Grade 3
- Any grade 2 toxicity unacceptable to the patient that requires a dose reduction
- Missing >30% of treatment doses for toxicity reasons
- Any other grade 3 or 4 effects thought to be treatment related

#### 3.1.1.3 HIV control

- The study subjects' HAART PK drug levels, HIV viral load and CD4 counts will be made available to their principal investigator and HIV physician immediately following analysis. Detrimental changes in HIV control considered at least possibly related to the study drug must be discussed with the trial management team HIV physician ([name]) and chief investigator ([name]). Persistent increases in HIV viral load above 200 copies/ml and/or clinically significant decreases in CD4 count will result in the subject discontinuing the study drug.
- As an early phase clinical trial with specific pharmacokinetic and pharmacodynamic endpoints, it is important that patients' HAART regimen is not be changed for their first 3 months on the trial (i.e. until after the C4D22/C5D1 visit) unless clinically necessary.

# 3.1.2 Maximum Tolerated Dose (MTD)

The MTD is defined as the highest dose producing one or less DLT in 6 patients. This dose will be used as the recommended phase II dose (RPTD). Phase I is now complete and the recommended phase II was determined to be 75 mg bd.

# 3.2 Phase II

Patients will be recruited in a single-arm study at the RPTD, in order to determine objective tumour response using AIDS Clinical Trials Group Oncology Committee (ACTG) criteria (see Appendix 1). Patients recruited to the RPTD during phase I will be included in the phase II study. KS will be evaluated using clinical photographs of target lesions and bi-dimensional measurements every 3 weeks and/or CT imaging of assessable disease sites every 6 weeks during treatment. As in phase I, patients who continue to respond to selumetinib following completion of 6 cycles of therapy will be offered the option of continuing selumetinib. Patients who have been shown to derive benefit from selumetinib and HAART combined therapy at one year should be continued on this regimen as long as there has been no disease progression and their risk: benefit analysis, in the opinion of the Chief Investigator and treating physician, favours the continuation of treatment and with approval from AstraZeneca. To continue treatment beyond 6 cycles sites should contact the SCART Trial Office as described in section 3.1. Patients' HAART regimen should not be changed for their first 3 months on the trial (i.e. until after the C4D22/C5D1 visit) unless clinically necessary. If deemed clinically necessary, sites should contact the SCART Trial office to facilitate discussion with the Chief Investigator and Clinical Co-Investigators.

# 4 ELIGIBILITY

### 4.1 Inclusion Criteria

- HIV positive and established on a HAART regimen for ≥ 3 months.
- · Histologically confirmed KS
- Measurable disease according to ACTG criteria.
- Progressive cutaneous or nodal KS not requiring chemotherapy OR progressive KS following cytotoxic chemotherapy.
- Evidence of disease progression in the past 6 months. No anti-cancer treatment within one month prior to commencing trial treatment.
- Adequate haematological function:
  - o Haemoglobin ≥ 9 g/dL
  - Absolute neutrophil count ≥ 1.5 x 10^9/L
  - o Platelets ≥ 100 x 10^9/L
- Adequate hepatic function:
  - Serum bilirubin ≤ 1.5 x upper limit of normal (ULN), except if the patient is established on the anti-retroviral drug atazanavir (no upper limit) and has AST and ALT levels ≤ 2.5 x ULN
  - ALT ≤ 2.5 x ULN
  - o AST ≤ 2.5 x ULN
- Adequate renal function:
  - o Serum creatinine clearance > 50 ml/min (Cockcroft-Gault formula or 24 hour urine collection).
- Age ≥ 18 years.
- World Health Organisation (WHO) performance status ≤ 2.
- For selumetinib, women of child bearing age and child bearing potential MUST have a negative
  pregnancy test prior to study entry AND be using an adequate contraception method, which must
  be continued while on treatment and for at least 4 weeks after the study treatment has ended.
- Male patients must agree to use an effective contraception method while on treatment and for at least 16 weeks after the study treatment has ended (barrier contraception is recommended for all individuals living with HIV).
- Written informed consent.

### 4.2 Exclusion Criteria

- HIV viral load > 200 copies/ml.
- Active opportunistic infections.
- · Active hepatitis B, hepatitis C.
- Any prior exposure to MEK, Ras, or Raf inhibitors or history of hypersensitivity to selumetinib, or any excipient agents.
- Any unresolved toxicity > CTCAE Grade 2 from previous anti-cancer therapy, except for alopecia
- Cardiac conditions as follows:
  - Uncontrolled hypertension (BP ≥150/95 mmHg despite medical therapy)
  - Left ventricular ejection fraction <55% measured by echocardiography

  - o Atrial fibrillation with a ventricular rate >100 bpm on ECG at rest
  - Symptomatic heart failure (NYHA grade II-IV)
  - Prior or current cardiomyopathy
  - Severe valvular heart disease
  - Uncontrolled angina (Canadian Cardiovascular Society grade II-IV despite medical therapy)
  - o Acute coronary syndrome within 6 months prior to starting treatment
- Major surgery within 4 weeks prior to starting selumetinib.
- Refractory nausea, vomiting, chronic gastrointestinal diseases (e.g. inflammatory bowel disease) or significant bowel resection that would preclude adequate absorption.

- Ophthalmological conditions as follows:
  - Intra-ocular pressure >21 mmHg, or uncontrolled glaucoma (irrespective of intra-ocular pressure)
  - Current or past history of central serous retinopathy or retinal vein occlusion
- Evidence of any psychological, familial, sociological or geographical condition potentially hampering protocol compliance.
- Treatment with any investigational product within 28 days of registration.
- Clinical judgement by the Investigator that the patient should not participate in the study.
- Pregnant or breast-feeding women.

#### 4.2.1 Asian Patients

Due to higher PK exposure, patients of Asian ethnicity may be at a higher risk of adverse events with selumetinib treatment. Selumetinib is not contra-indicated in patients of Asian ethnicity, but the potential increased risk of toxicity should be considered and included as part of the discussion with the patient prior to receiving informed consent (see section 7.3.1.1 for further details).

# 5 PATIENT SCREENING AND CONSENT

# 5.1 Screening

Potentially eligible HIV positive patients with confirmed progressive KS on an established HAART regimen (≥ 3 months) can be screened for entry into this trial. For patients who appear to meet the criteria for participation in the trial, the Investigator will provide information to allow them to make an informed decision regarding their participation. If informed consent is given, the Investigator will conduct a full screening evaluation to ensure that the patient satisfies all inclusion and exclusion criteria. A patient who gives written informed consent and who satisfies all the inclusion and exclusion criteria may be entered into the trial. Patients should only be approached about the trial if there is a slot available. Investigators must keep a screening log of all patients who receive a patient information sheet.

# 5.1.1 Patient Screening Log

The following details of all patients screened for participation in this study will be collected:

- Date screened
- Date of birth
- Gender
- Whether the patient was eligible and reasons for ineligibility
- Whether the patient gave written informed consent
- Whether the patient was registered
- Reason(s) patient was not registered

## 5.2 Informed Consent

It is the responsibility of the Investigator to obtain written informed consent for each patient prior to performing any trial related procedure. A Patient Information Sheet (PIS) is provided to facilitate this process. Investigators must ensure that they adequately explain the aim, trial treatment, anticipated benefits and potential hazards of taking part in the trial to the patient. The Investigator should also stress that the patient is completely free to refuse to take part or withdraw from the trial at any time. The patient should be given ample time (at least 24 hours) to read the PIS and to discuss their participation with others outside of the site research team. The patient must be given an opportunity to ask questions which should be answered to their satisfaction. The right of the patient to refuse to participate in the trial without giving a reason must be respected.

If the patient wishes to participate in the trial they should be asked to sign and date the latest version of the Informed Consent Form (ICF) in the presence of the Investigator or designee who must then co-sign

and date the form. The patient must personally initial all the boxes. A copy of the ICF should be given to the patient, a copy should be filed in the hospital notes, and the original placed in the Investigator Site File (ISF). Once the patient is entered into the trial the patient's registration number should be entered on the ICF maintained in the ISF.

Details of the informed consent discussions should be recorded in the patient's medical notes, this should include date of, and information regarding, the initial discussion, the date consent was given, with the name of the trial and the version number of the PIS and ICF. Throughout the trial, the patient should have the opportunity to ask questions about the trial and any new information that may be relevant to the patient's continued participation should be shared with them in a timely manner. On occasion it may be necessary to re-consent the patient in which case the process above should be followed and the patient's right to withdraw from the trial respected.

Electronic copies of the PIS and ICF are available from the Trial Office and should be printed or photocopied onto the headed paper of the local institution. Details of all patients approached about the trial should be recorded on the Patient Screening/Enrolment Log and with the patient's prior consent the physician co-ordinating their medical care (i.e. their General Practitioner (GP) and/or HIV Physician) should also be informed that they are taking part in the trial. If the patient does not consent to their GP being informed, then their HIV clinician should be informed instead. A GP/HIV clinician Letter is provided electronically for this purpose.

# **6 TRIAL ENTRY**

Prior to recruitment of patients into the study, the Principal Investigator for each site, or their designee, should have returned all required documentation to the SCART Trial Office, and the site personnel involved with the SCART study must have received appropriate training from the Trial Coordinator. Patients must be registered with the CRCTU at the University of Birmingham. Before approaching a potential patient, Investigators should check that there is a slot available with the SCART Trial Office. The patient's eligibility will be confirmed at registration. If eligible for the study, the patient will be allocated a Registration Number and dose. Study drug prescriptions must include the patient's Registration Number and allocated dose level. The registration line will be open during office hours (9am-5pm, Monday-Friday).

Registration Line: [name] or [name]

# 7 TREATMENT DETAILS

# 7.1 Selumetinib

The Investigational Medicinal Product in this trial is selumetinib. The starting dose of selumetinib for each patient will be released with their Registration Number. Selumetinib should be taken twice daily approximately 12 hours apart with water, at least 2 hours after a meal and 1 hour before the next meal. Selumetinib capsules will be administered in doses as described in section 3 in a continuous 21 day cycle, unless disease progression (see section 7.4) or unacceptable toxicity is encountered. The trial design, dose levels and numbers of required patients are shown in section 3.1.

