# 7.4.2 Non-Haematologic Adverse Events (including biochemistry/hepatic/renal function)

Grade of	Management/Next Dose for Selumetinib							
Event								
grade 1	no change in dose							
grade 2	Hold until ≤ grade 1∞ – resume at same dose, except for rash where							
	CTCAE grade 2 rash is acceptable							
grade 3	Hold* until < grade 2 – resume at 1 dose level lower if indicated,**							
	except for rash where patients with CTCAE grade 2 rash may restart							
	treatment (unless defined as a DLT).							
grade 4	Off protocol therapy							
								

- \* Patients requiring a delay of > 2 weeks should go off protocol therapy.
- \*\* Patients requiring > 2 dose reductions should go off protocol therapy.
- ∞Please refer to Appendix 10 for management of elevated creatine kinase

7.5 The dose modification algorithm allows for the following dose reductions:

75mg bd  $\rightarrow$  50mg bd  $\rightarrow$  75mg od

returns will be disposed of by Pharmacy according to local hospital practice. Further information can be found in the Pharmacy Manual (supplied separately).

CRCTU

Treatr

at the

es

ug

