# 7.6 Overdose

There is currently no known antidote to selumetinib. Adverse reactions associated with overdose should be supportive for the underlying symptoms. Doses of study treatment in excess of that specified in the clinical study protocol are considered to be an overdose. Should an overdose (accidental or deliberate) occur, all symptoms associated with the overdose should be reported as AEs.

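### Section 7.1 gives a twice-daily instruction with no exception, but dose level -1 and the second permitted dose reduction are once daily

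*Protocol*

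**What the plan says.** Section 7.1 is where the protocol says how the drug is taken: "Selumetinib should be taken twice daily approximately 12 hours apart with water". No dose level is exempted. The next sentence refers elsewhere for the amounts: "Selumetinib capsules will be administered in doses as described in section 3 in a continuous 21 day cycle".

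The dose table in section 3.1 lists the levels with a frequency and a daily total. Level 1 is "50 mg bd (100 total" mg), level 2 is "75 mg bd (150 total" mg) and level -1 is "75 mg od (75 total" mg). The abbreviation list defines od as once a day and bd as twice a day.

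Section 3.1.2 fixes the dose for the current phase: "Phase I is now complete and the recommended phase II was determined to be 75 mg bd". After the table in section 7.4.2 the protocol states "The dose modification algorithm allows for the following dose reductions" and gives 75 mg bd, then 50 mg bd, then 75 mg od. A patient who needs more than two reductions goes off protocol therapy, so 75 mg od is the last step on treatment.

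Section 7.6 adds: "Doses of study treatment in excess of that specified in the clinical study protocol are considered to be an overdose".

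**The concern.** One dose level in the protocol is taken once daily, and the administration section allows for no such level. At that level a site cannot follow both section 7.1 and the dose table.

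The level is still in use. No phase I cohort will be opened again at level -1, but a phase II patient starts at 75 mg bd and reaches 75 mg od at the second reduction. Anyone at that step has already been reduced twice for toxicity. If the conflict led to a dosing error, these are the patients it would affect.

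**Working it through.** **Inputs.** Amounts, frequencies and daily totals come from the section 3.1 table. The meanings of od and bd come from the abbreviation list, the reduction sequence from section 7.4.2, the phase II dose from section 3.1.2, and the capsule strength (25 mg) from section 7.7.

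**Step 1: reproduce the plan's own totals.** Daily total = mg per administration × administrations per day, with od = 1 and bd = 2.

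| Level | Dose | Calculated | Stated |
|---|---|---|---|
| -1 | 75 mg od | 75 × 1 = 75 mg | 75 mg |
| 1 | 50 mg bd | 50 × 2 = 100 mg | 100 mg |
| 2 | 75 mg bd | 75 × 2 = 150 mg | 150 mg |
| 3 | 100 mg bd | 100 × 2 = 200 mg | 200 mg |

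All four agree, so the table is consistent within itself.

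**Step 2: the reduction sequence.** From the phase II dose the daily totals are 150, then 100, then 75 mg. The sequence falls at each step, as a reduction sequence should.

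**Step 3: apply the section 7.1 frequency at each level.** For levels 1, 2 and 3 a twice-daily frequency leaves the total unchanged (ratio 1.0). For the 75 mg od step it gives 75 × 2 = 150 mg per day against a stated 75 mg, a ratio of 150 / 75 = 2.0. The result equals the unreduced phase II dose, 75 × 2 = 150 mg. The amount exceeds what sections 3.1 and 7.4.2 specify, so section 7.6 would class it as an overdose, although the frequency follows section 7.1.

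**Step 4: can both texts be met by splitting the daily total?** Two equal doses would be 75 / 2 = 37.5 mg each, which is 37.5 / 25 = 1.5 capsules. Equal doses of whole capsules cannot deliver this, and the protocol describes no other split. The conflict is therefore one of substance at this level and cannot be read away as a difference in wording.

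**The case against.** The best reply is that no careful reader would be misled. The specific dose entry governs the general sentence. Section 3.1 prints both the once-daily abbreviation and the 75 mg total, and section 7.4.2 repeats the abbreviation. Section 7.1 itself sends the reader to section 3 for the doses. The twice-daily sentence follows one about each patient's starting dose, and it is correct for the phase II starting dose. Section 6 requires prescriptions to carry the allocated dose level. The Pharmacy Manual and the labels, which are not shown, may state the frequency.

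Most of this stands, and it limits the point. A reader might infer that a patient reduced twice would take double the intended dose. The documents do not support that: it happens only if someone ignores both the abbreviation and the printed total.

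The reply does not remove the contradiction. The reference to section 3 concerns doses and does not qualify the stated frequency. In section 3 the once-daily dose appears only as a phase I level; the reduction sequence that applies in phase II is in section 7.4.2, to which section 7.1 does not refer for reduced doses. Section 6 speaks of the dose allocated at registration and does not say how frequency is restated after a reduction.

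Two further inferences are tempting and should not be drawn:

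- **A count of affected patients built from the grade 3 or higher rates in section 7.3.1.** Those are only the most commonly reported events. A grade 3 event leads to a lower dose only where indicated, and a grade 4 event takes the patient off protocol therapy. No count follows from them.
- **An ambiguous denominator for missed doses or dose intensity.** The missed-dose threshold in section 3.1.1.2 is a dose-limiting toxicity criterion, and section 3.1.1 confines those to cycle 1 of phase I, which is complete. For dose intensity, the planned daily total of 75 mg is printed, and the method of calculation may properly be left to the SAP.

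**Conclusion.** The administration instruction in section 7.1 is wrong as written for one dose level: it contradicts the section 3.1 table and the section 7.4.2 reduction sequence at 75 mg od. The point is minor. It concerns only phase II patients at the second reduction, whose number is not given.

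The factor of 2 (150 against 75 mg per day) is conditional on the twice-daily sentence being applied to the 75 mg amount. It measures the size of a possible error and is not a forecast of what sites will do. The trial's design, sample size and analysis are unaffected. No view is taken here on which frequency is right; the passages must be made to agree.

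**What to change.** The sponsor should reconcile sections 7.1, 3.1 and 7.4.2. The simplest route is to tie the frequency in section 7.1 to the patient's allocated or reduced dose level, with a reference to both the dose table and the reduction sequence, so that each level has one stated frequency throughout. The sponsor decides what that frequency is. Patient instructions, the Pharmacy Manual and labels should then be checked against it.

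The cost is about one sentence in section 7.1 and a check of the supporting documents. Nothing changes in the analysis.
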